**Development of Culturally Sensitive and
Patient-Centered Feedback for Alzheimer's
Dementia Risk Disclosure**

NCT04309500

IRB Approval Date: January 26, 2022

Uploaded: 09/29/2022

Intervention:	
Stage I: Observational study (needs assessment); no intervention
 
Stage II: Behavioral Intervention: personalized Dementia-Alzheimer's type risk disclosure feedback

Key Inclusion Criteria:	
Stage I: Human volunteers who are consensus diagnosed as cognitively healthy or with Mild Cognitive Impairment (MCI) with ability to consent; ≥ 65 years of age; first-language English; identified co-participant who is cognitively healthy, has known the participant for ≥ 5 years, and has at least weekly phone/in-person contact with the participant
 
Stage II: Same as Phase I, plus participants must have a negative baseline screen for clinically significant depression or anxiety on standardized measures and already be followed by a medical provider.

Key Exclusion Criteria:	Stage I & II: Significant uncorrected sensory impairment, severe neurologic or psychiatric diagnosis; consensus diagnosis of dementia
Study Type:	Interventional, single-group design
Primary purpose:	
Stage I: Complete assessment of needs, preferences, and rationale regarding DAT risk disclosure in participants and their family members of diverse racial-ethnic backgrounds
 
Stage II: Develop and pilot personalized DAT risk disclosure protocols with participants and family members of diverse racial-ethnic backgrounds; investigate initial outcomes including comprehension/recall of results, satisfaction, and psychological reactions immediately following risk disclosure and at 1- and 6-weeks following risk disclosure

Phase:	I/II (Stage II Behavioral Intervention Study)
Date of First Enrollment:	
Stage I: 10/22/19
 
Stage II: 10/1/20 (anticipated)

Target Sample Size:	
Stage I: up to 120 (60 participant/co-participant dyads)
 
Stage II: 20 (10 participant/co-participant dyads)

Recruitment Status:	
Stage I: Currently recruiting
 
Stage II: Currently recruiting

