3.1.1 Stage I

Participants (those identified as the person who would hypothetically receive DAT risk feedback) will be recruited from the Michigan Alzheimer's Disease Research Center's University of Michigan Memory and Aging Project (UM-MAP), Testing High Definition transcranial Direct Current Stimulation (HD-tDCS) as Treatment of Mild Cognitive Impairment Project (STIM), or Dementia in African American Population Phenotyping from Potential Elevated Risk (DAPPER) project.

Participants will include up to 60 older adults, age 65+ years who have completed an initial evaluation as part of the University of Michigan Memory and Aging Project (UM-MAP), the Testing High Definition transcranial Direct Current Stimulation (HD-tDCS) as Treatment of Mild Cognitive Impairment (STIM) project, or as part of the Dementia in African American Population Phenotyping from Potential Elevated Risk (DAPPER) project. Consistent with the diversity-related goals of this study, 25 of these participants will be self-reported Non-Hispanic African-American, and 25 will be self-reported Non-Hispanic White. As exploratory analyses will look at the role of cognitive impairment, approximately 50% of the sample will be consensus-diagnosed as either cognitive healthy or with Mild Cognitive Impairment (MCI; single- or –multiple domain, amnesic or non-amnesic forms) through their participation in UM-MAP, STIM, or DAPPER. Exclusion criteria include current or historical neurologic disorder (e.g., Alzheimer's dementia or other neurodegenerative dementia, Parkinson's disease, seizure disorder, tumor, multiple sclerosis) or neurologic injury (e.g., significant stroke or moderate-severe head injury, defined by loss of consciousness > 5 minutes, presence of significant post-traumatic amnesia, or the need for extended hospitalization or intervention). Participants with motor symptoms indicative of a neurodegenerative etiology other than Alzheimer's disease will also be excluded. Participants with severe mental illness (i.e., bipolar disorder, thought disorder, psychosis) or anyone deemed to meet criteria for current substance use disorder will be ineligible for participation in this study.

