In March 2020, the global Covid-19 pandemic resulted in research ramp-down and restrictions on in-person research visits. To protect the health of our participants, particularly given their vulnerable status as older adults, we determined that it would be best not to continue in-person research visits, and to instead adapt this protocol to allow for virtual visits. Therefore, during telephone screening, participants will be offered the opportunity to complete the Stage I session as a video or phone visit. Interested participants will be asked whether they have adequate access to and familiarity with a laptop, tablet, or computer to engage in a video visit session in which they will complete questionnaires and interviews using video-conferencing software. Participants who do not have access to this technology or do not feel comfortable completing the visit over video will be offered the opportunity to complete the session over the phone. Those that decline phone or video visit, but remain interested in the study will be deferred for scheduling until a time that it is deemed safe by research administration for participants to engage in in-person research.

In-Person Sessions: At the initiation of the session, participants/co-participants will complete written informed consent and the decision-making tool to ensure that they are cognitively capable of doing so. Additional screening criteria will then be reviewed. Co-participants without recent neuropsychological or cognitive evaluation (within 6 months) will also be screened using the MoCA.

Video Conferencing Sessions: Participants and Co-Participants who are interested in engaging in a video visit will be asked about their access to and comfort with technology for the session prior to scheduling. Participants and Co-Participants must utilize a desktop or laptop computer, or a tablet with a screen at least 9.7 inches in diagonal width to ensure that they are able to view the questions completely. Additionally, participants/co-participants must have access to a stable, secure internet connection (not public wi-fi) and a quiet, private space where they will be uninterrupted for the duration

Figure 1.
Stage I
Timeline of
Activities

of the 2-hour appointment. Participants and Co-Participants who meet the above criteria will be sent separate links to engage in a secure video conference session through the BlueJeans or Zoom for Health applications. Both applications are free, HIPAA-compliant services.

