3.4.2 Statistical Design

Data Screening (Stage I & II)

Prior to statistical analyses, data screening will be conducted. Initial steps will include a missing data analysis to determine randomness of missing data and range checks to assess for data quality. Additional screening for univariate and multivariate outliers, skewness and kurtosis will be conducted to inform needs for data transformation and statistical approach. Additionally, for Stage I data, we will compare outcomes in participants who completed in-person vs. video vs. phone visits to ensure that session modality did not impact interpretation of results.

Statistical Approach

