3.4.2.1 Stage I

Primary Outcome 1.1 (Differences in risk disclosure interest and preferences): To analyze the dichotomous yes/no interest outcomes, chi-squared analyses will be used to compare the proportion of African-American and White participants who endorse interest in receiving feedback at each level, for caregivers and patients separately. Given that there are five levels of risk disclosure feedback, five comparisons will be conducted; to account for the relatively small sample size, a conservative Bonferroni correction for multiple comparisons will be implemented ($\alpha = .05/5 = .01$). To analyze the Likert-style interest outcomes, either independent samples *t*-tests or Mann Whitney U tests will be used to compare mean interest level in African-American and White participants for each of the five risk disclosure levels, again using a Bonferroni correction. Further exploratory correlation analyses will determine agreement between caregiver and informant interest in African-American and White subgroups, separately.

Primary Outcome 1.2 (Differences in risk disclosure rationale): This study will assess whether African-American and White participants and co-participants identify different primary reasons for risk disclosure (i.e., basic curiosity, emotional reason, financial planning, medical planning, legal planning, social/family planning, or other), a Fisher's Exact test will be used, comparing frequency of reason endorsement. These analyses will be conducted for patients and informants separately; however, we will also explore agreement among dyad members.

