Primary Outcome 1.3 (Patient characteristics that influence preferences): We will utilize a regression approach to determining patient characteristics and perspectives that shape level of interest. More specifically, we will create mixed linear models to quantify the fixed effects of four sets of variables (participant factors [demographics, baseline anxiety and depression, DAT knowledge], ADI Perceived threat of DAT, ADI Perceived benefits of this level of risk disclosure, ADI Perceived barriers to using this risk information), as well as the random effects attributable to the dyadic relationship. This approach will allow us to calculate the intra-class correlations representative of the effect of the dyadic relationship. Furthermore, given the likely effect of dyadic role ('patient' or informant) on perceived threat, perceived benefits, and perceived barriers, the interaction terms (e.g., role by threat, role by benefits, role by barriers) will also be included in the model. It is expected that the effect of the dyadic relationship will be significant; therefore, additional subgroup analyses examining predictors of risk disclosure interest in caregivers and patients *separately* will be conducted.

Primary Outcome 1.4 (Differences in importance of risk disclosure components): To analyze the Likert-style importance outcomes, either independent samples *t*-tests or Mann Whitney U tests will be used to compare mean interest level in African-American and White participants for each of the feedback components, again using a Bonferroni correction. Further exploratory correlation analyses will determine agreement between caregiver and informant interest in African-American and White subgroups, separately.

Secondary Outcome (Qualitative Information from Semi-Structured Interviews): In combination with the semi-structured interviews, we will therefore record and transcribe the narrative responses of patients and caregivers. After basic 'cleaning' of the data (removal of articles, non-content utterances, and additional identified 'stop' words), the text will be analyzed using R Statistical Software for most commonly used words or phrases by race. A Topic Modeling approach (akin to an exploratory factor analysis for text analysis) will be utilized to identify central themes (the 'factors') and associated terms or phrases (the 'items') by race.

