4.3 Adverse Events Reporting: Participant mood and distress will be carefully assessed for the 50 Year I dyads using the Geriatric Depression Scale – 15 Item version (GDS-5) and the Beck Anxiety Inventory (BAI). These measures, in addition to the Impact of Event Scale (IES), will be administered to the patient and informant dyads receiving pilot feedback in Year 2 to determine (a) whether changes in mood or distress occur, and (b) whether these changes are attributed to study participation. The GDS and BAI have empirically supported cut-off scores for determining clinically significant depression, anxiety; scores will therefore be used to define the nature of any events (unanticipated vs. anticipated, adverse vs. serious adverse) and relationship of these events to study participation (related vs. unrelated). The IES does not have a validated cutoff; however, we will treat a score of 24 or higher as warranting additional study team follow-up.

Information regarding non-serious adverse events (i.e., an elevation in mood or anxiety symptoms as a result of study participation) will be reported directly to the PI, who will compile and submit a report to independent Safety Officer (SO). The SO for this project is [name] ([contact]). Similarly, serious adverse events that are determined to be unrelated to study participation will be reported to the PI, recorded in a secure study database, and reported to the SO. These summary reports will be submitted to the SO on a quarterly basis.

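### The Stage I visit-modality check is too small to establish that modality did not matter, and the race analyses should carry a modality-adjusted sensitivity estimate whatever it shows

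*Combined protocol and SAP*

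**What the plan says.** Modality enters the analysis plan once. Under Data Screening in section 3.4.2, Stage I data will be used to "compare outcomes in participants who completed in-person vs. video vs. phone visits to ensure that session modality did not impact interpretation of results". No test, significance level, margin or consequence of a difference is given, nor whether participants and co-participants are checked separately or together.

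Modality was not allocated. The summary table dates first Stage I enrollment to 22 October 2019. Section 3.3.1 reports that, after the March 2020 restrictions, "we determined that it would be best not to continue in-person research visits, and to instead adapt this protocol to allow for virtual visits". Phone visits are for those without the equipment for video or not at ease with it. People who decline both are deferred until in-person work is judged safe.

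The race analyses are in section 3.4.2.1. For Outcome 1.1, "chi-squared analyses will be used to compare the proportion of African-American and White participants who endorse interest in receiving feedback at each level", separately by role, with t or Mann–Whitney tests for the Likert ratings and alpha of 0.05/5 = 0.01. Outcome 1.2 uses Fisher's exact test, and Outcome 1.4 uses t or Mann–Whitney tests. None is adjusted. The only regression, Outcome 1.3, lists "participant factors [demographics, baseline anxiety and depression, DAT knowledge" and three sets of ADI scores. Neither modality nor enrollment period is named.

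On size, the summary table gives "up to 120 (60 participant/co-participant dyads", section 3.1.1 says "25 of these participants will be self-reported Non-Hispanic African-American, and 25 will be self-reported Non-Hispanic White", and section 4.3 refers to 50 dyads. Each role therefore has 50 to 60 people.

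**The concern.** A comparison that finds no difference supports a claim of no effect only if it could have found a difference worth worrying about. Three groups drawn from 50 to 60 people give wide intervals, so a moderate modality effect can easily go unseen.

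This matters because modality is not a random label. In-person versus remote largely follows calendar time, before and after the pandemic restrictions. Video versus phone follows access to and comfort with technology. If either is distributed differently between African-American and White participants, part of a modality effect would appear in the race contrast, creating a difference or hiding one. The check is the only protection the plan offers.

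**Working it through.** **Plan's own figure.** The only computed design figure here is the Bonferroni level for Outcome 1.1: 0.05/5 = 0.01, which reproduces. The plan gives no power figure for the modality check or the race contrasts.

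**Inputs.** From the documents: 50 to 60 people per role; 25 per race; alpha 0.01 for the 1.1 race contrasts. Assumed, because the documents do not give them: 10 to 20 people per role seen in person; effects of 0.5 and 0.8 SD; two-sided tests; alpha 0.05 for the modality check; the in-person share by race.

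**1. Power of the check, in-person versus remote.** Two-sample t-test, noncentrality = d × √(n₁n₂/(n₁+n₂)).

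| In person / remote | Noncentrality, d = 0.5 | Power, d = 0.5 | Power, d = 0.8 |
|---|---|---|---|
| 10 / 40 | 0.5 × √8.00 = 1.41 | 28% | 60% |
| 15 / 35 | 0.5 × √10.50 = 1.62 | 36% | 72% |
| 20 / 40 | 0.5 × √13.33 = 1.83 | 43% | 82% |

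Across these splits the effect detectable with 80% power is 0.78 to 1.01 SD. The 95% confidence interval half-width, 1.96 × √(1/n₁ + 1/n₂), runs from 0.54 SD (20/40) to 0.69 SD (10/40).

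The comparison as described has three groups. With an in-person effect of 0.5 SD and video equal to phone, one-way ANOVA has 21–34% power; at 0.8 SD it has 49–72%. The two-group figures are therefore the more favorable ones.

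**2. What showing no effect would need.** With an assumed equivalence margin of 0.5 SD, 5% per side and 80% power, n per group = 2 × (1.645 + 1.282)² / 0.5² ≈ 69. One role has at most 60 people in all.

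**3. Bias in a race contrast if modality is ignored.** Bias = modality effect × difference between races in the in-person share.

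- Equal shares: zero.
- 0.5 SD, 20 points: 0.5 × 0.20 = 0.10 SD.
- 0.5 SD, 40 points (for example 60% versus 20%): 0.5 × 0.40 = 0.20 SD. With 25 per race, the type I error at nominal 0.01 becomes about 0.03.
- 0.8 SD, 60 points: 0.8 × 0.60 = 0.48 SD. The type I error becomes about 0.16.

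**4. Precision after adjustment.** With 25 per race, the unadjusted SE is √(2/25) = 0.283 SD. Assuming 40% in person overall, φ² = Δp² × 0.25/(0.4 × 0.6), and the adjusted SE is 0.283 × √(1/(1 − φ²)).

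| Imbalance Δp | φ² | Variance inflation | Adjusted SE (SD) |
|---|---|---|---|
| 0 | 0 | 1.00 | 0.283 |
| 20 points | 0.042 | 1.04 | 0.289 |
| 40 points | 0.167 | 1.20 | 0.310 |
| 60 points | 0.375 | 1.60 | 0.358 |

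**5. Why not separate strata.** With 60% versus 20% in person and 25 per race, the strata are 15 versus 5 and 10 versus 20. Power for a 0.8 SD race difference at alpha 0.01 is 12% and 26%, against 56% in the unstratified comparison. A single adjusted estimate avoids most of that loss.

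**The case against.** The strongest reply is that confounding with race is conjecture. The documents give no modality split, no modality-by-race table and no enrollment dates by race, and section 3.1.1 sets equal race targets with no sequence. That stands. A reader might infer that the planned race comparisons are confounded by modality; the documents show only that they could be.

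A reader might also infer that any real modality effect would slip through. That is not supported. At 0.8 SD the check would more likely detect the effect than miss it (60–82% per role for in-person versus remote), and pooling both roles does better still (81–96% for the three-group test, optimistic because it ignores correlation within dyads). The weakness concerns moderate effects.

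Nor does the plan say that a null result closes the question. It says only that outcomes will be compared, without naming a significance test, so a claim that it treats modality as disposed of would rest on its silence. What remains is that the stated purpose is more than such a comparison can deliver, and no adjusted race analysis follows.

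The calendar link is also partial: it applies to in-person versus remote, and deferred people may be seen in person later. Finally, Stage I is an observational needs assessment, and the Stage II results are descriptive and not subject to this check.

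**Conclusion.** The point holds in limited form and is of low priority. The comparison cannot establish that modality did not matter: power for a 0.5 SD in-person versus remote effect is about 28–43% per role, under assumed splits with 10 to 20 people in person. The race analyses do not adjust for modality, although its levels are linked to calendar time and to technology access.

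Whether the race contrasts are biased is unknown. The range of 0.10–0.48 SD is conditional on assumed effects of 0.5–0.8 SD and imbalances of 20–60 points; the bias is zero if shares are equal. For scale, the SE of a race contrast with 25 per group is 0.283 SD. Because the check already requires modality to be recorded, a modality-adjusted sensitivity analysis is a better safeguard than the check alone, at small cost.

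**What to change.** In section 3.4.2:

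- Replace the aim of ensuring no impact with estimated modality differences and 95% confidence intervals.
- Tabulate all three modality levels by race, for each role.

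In section 3.4.2.1:

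- Add in-person versus remote as a covariate in the Outcome 1.3 model.
- Whatever the check shows, report one modality-adjusted sensitivity estimate of each Outcome 1.1 and 1.4 race contrast, from linear or logistic regression. A Mantel–Haenszel or van Elteren test is an alternative. Do not test within separate strata.
- Tabulate Outcome 1.2 by modality.
- Where numbers allow, add a video versus phone term, since the in-person versus remote term does not cover technology access.

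No new data are needed. The SE of a race contrast rises from 0.283 to 0.289–0.310 SD for a 20–40 point imbalance, and to 0.358 SD for 60 points. Adjustment cannot separate modality from calendar period, and the report should say so.

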3.4.2.1 Stage I

Primary Outcome 1.1 (Differences in risk disclosure interest and preferences): To analyze the dichotomous yes/no interest outcomes, chi-squared analyses will be used to compare the proportion of African-American and White participants who endorse interest in receiving feedback at each level, for caregivers and patients separately. Given that there are five levels of risk disclosure feedback, five comparisons will be conducted; to account for the relatively small sample size, a conservative Bonferroni correction for multiple comparisons will be implemented ($\alpha = .05/5 = .01$). To analyze the Likert-style interest outcomes, either independent samples *t*-tests or Mann Whitney U tests will be used to compare mean interest level in African-American and White participants for each of the five risk disclosure levels, again using a Bonferroni correction. Further exploratory correlation analyses will determine agreement between caregiver and informant interest in African-American and White subgroups, separately.

Primary Outcome 1.2 (Differences in risk disclosure rationale): This study will assess whether African-American and White participants and co-participants identify different primary reasons for risk disclosure (i.e., basic curiosity, emotional reason, financial planning, medical planning, legal planning, social/family planning, or other), a Fisher's Exact test will be used, comparing frequency of reason endorsement. These analyses will be conducted for patients and informants separately; however, we will also explore agreement among dyad members.

Primary Outcome 1.3 (Patient characteristics that influence preferences): We will utilize a regression approach to determining patient characteristics and perspectives that shape level of interest. More specifically, we will create mixed linear models to quantify the fixed effects of four sets of variables (participant factors [demographics, baseline anxiety and depression, DAT knowledge], ADI Perceived threat of DAT, ADI Perceived benefits of this level of risk disclosure, ADI Perceived barriers to using this risk information), as well as the random effects attributable to the dyadic relationship. This approach will allow us to calculate the intra-class correlations representative of the effect of the dyadic relationship. Furthermore, given the likely effect of dyadic role ('patient' or informant) on perceived threat, perceived benefits, and perceived barriers, the interaction terms (e.g., role by threat, role by benefits, role by barriers) will also be included in the model. It is expected that the effect of the dyadic relationship will be significant; therefore, additional subgroup analyses examining predictors of risk disclosure interest in caregivers and patients *separately* will be conducted.

Primary Outcome 1.4 (Differences in importance of risk disclosure components): To analyze the Likert-style importance outcomes, either independent samples *t*-tests or Mann Whitney U tests will be used to compare mean interest level in African-American and White participants for each of the feedback components, again using a Bonferroni correction. Further exploratory correlation analyses will determine agreement between caregiver and informant interest in African-American and White subgroups, separately.

Secondary Outcome (Qualitative Information from Semi-Structured Interviews): In combination with the semi-structured interviews, we will therefore record and transcribe the narrative responses of patients and caregivers. After basic 'cleaning' of the data (removal of articles, non-content utterances, and additional identified 'stop' words), the text will be analyzed using R Statistical Software for most commonly used words or phrases by race. A Topic Modeling approach (akin to an exploratory factor analysis for text analysis) will be utilized to identify central themes (the 'factors') and associated terms or phrases (the 'items') by race.

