1.1 Do African-American and White participants or co-participants differ in their interest in receiving certain types of DAT risk information? The study will evaluate group differences in participant and co-participant interest in and actual preference for feedback at five levels: (1) no information about AD risk, or risk information based on (2) standard clinical measures, (3) genetic information, (4) quantitative structural neuroimaging, (5) amyloid and tau PET. Exploratory analyses will assess whether group differences also exist based on clinical research diagnosis (normal vs. MCI), and whether participants and their co-participants agree.

1.2 Do African-American and White participants or co-participants differ in their perspectives on/rationale for certain types of DAT risk feedback? This study will assess whether African-American and White participants and co-participants identify different primary reasons for risk disclosure (i.e., basic curiosity, emotional reason, financial planning, medical planning, legal planning, social/family planning, or other). Exploratory analyses will assess whether group differences also exist based on clinical research diagnosis (normal vs. MCI), and whether participants and their co-participants agree.

1.3 Which characteristics predict risk disclosure interest in African-American vs. White participants and co-participants? This study will evaluate whether African-American and White participants and co-participants differ in their perceived threat of DAT, perceived benefits of risk disclosure, and perceived barriers to using risk information. We will also determine whether different factors (including personal demographic characteristics and the aforementioned perceived threat, benefits, and barriers) predict risk disclosure interest in different groups. Exploratory analyses will assess whether group differences also exist based on clinical research diagnosis (normal vs. MCI), and whether participants and their co-participants agree.

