HBM Components. We have developed the Anticipatory Dementia Inventory (ADI), a 50-item Likert-style measure of DAT-specific worry based on the HBM. Items relate to perceived vulnerability to DAT, perceived seriousness of a diagnosis, and expectations about ability to deal with a diagnosis, with responses ranging from strongly disagree to strongly agree. This measure has previously been validated for use with racially diverse older adults through the PI’s graduate work (paper in preparation).

Knowledge of AD/DAT. DAT knowledge will be measured through a multiple-choice quiz about DAT symptoms, course, causes, treatments, and risk factors. This quiz will be developed in Quarter 1 of the first funding year via monthly study-team meetings.

Risk Disclosure Interest and Preferences. In addition to the open-ended preference/rationale questions administered in the interview, we will utilize a questionnaire asking participants and co-participants to rate their level of interest in receiving feedback based on each risk factor (Table 3; e.g., “How interested are you in knowing about your/your family member’s risk for Alzheimer’s Dementia based on your genotype?”), on a continuous scale ranging from 1 (no interest) to 5 (very interested). Participants and co-participants will also use a checklist to state which information they would want to receive, selecting as many of the DAT risk information sources as desired (e.g., “Would you choose to receive feedback about your/your family member’s risk for DAT based on genotype? Yes or No?”)

Risk Disclosure Rationale. Participants will also be provided with a list of reasons for risk disclosure cited in prior literature and asked to rank the primary reason/purpose for risk disclosure.

Importance of Risk Disclosure Elements. Participants and co-participants will also complete a questionnaire asking them to rate the importance of different empirically supported elements of risk disclosure protocols cited in the published literature (e.g., How important do you think it is that educational materials are provided as part of your risk disclosure feedback?). Responses will be on a continuous scale from 1 (not at all important) to 5 (extremely important).

The order of questionnaires and interview questions will be counter-balanced to avoid potential reciprocal priming effects (e.g., discussing perceived vulnerability to DAT may influence feedback preferences).

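### Outcome 1.1 sets its threshold at .05/5 for five comparisons, but plans ten yes/no tests plus rating tests with no stated divisor; 5% control holds only within one role and one measure

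*Combined protocol and SAP*

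**What the plan says.** Section 3.4.2.1, Primary Outcome 1.1, covers two measures of interest in risk feedback.

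- **Yes/no items.** The plan says "chi-squared analyses will be used to compare the proportion of African-American and White participants who endorse interest in receiving feedback at each level", and adds that this is done "for caregivers and patients separately".
- **Threshold.** The next sentence reads "Given that there are five levels of risk disclosure feedback, five comparisons will be conducted". It then sets a Bonferroni alpha of .05/5 = .01, which it calls conservative.
- **1-to-5 ratings.** A t-test or Mann-Whitney test is planned "to compare mean interest level in African-American and White participants for each of the five risk disclosure levels, again using a Bonferroni correction". No divisor is given, and the split by role is not repeated.

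Two other places bear on who is tested. Section 2.2, question 1.1, states: "The study will evaluate group differences in participant and co-participant interest in and actual preference for feedback at five levels". Section 3.3.1 describes the rating questionnaire as "asking participants and co-participants to rate their level of interest in receiving feedback based on each risk factor". The agreement analyses within dyads are labelled exploratory and are not counted here.

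**The concern.** The count of five is the only reason given for the .01 threshold, and it does not match the tests described one sentence earlier. The plan declares no family of tests. A reader cannot tell whether 5% is meant to hold for one role on one measure, for one measure, or for Outcome 1.1 as a whole. For the ratings, the threshold itself cannot be worked out from the text.

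At stake is how a significant race difference in this primary outcome should be read. If the .01 threshold is taken to protect all the yes/no comparisons, the chance of at least one false race difference is higher than a reader would assume. An undeclared family also leaves the choice of threshold open until after the data are seen.

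**Working it through.** **Inputs from the documents (section 3.4.2.1 unless noted).** Nominal alpha .05; stated divisor 5; five levels; two roles for the yes/no items; two measures; 25 African-American and 25 White participants (section 3.1.1).

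**Assumptions.** Two-sided tests, because sidedness is not stated. The correlations and the interest rates used for power are also assumed; the documents give neither.

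**1. The plan's own figure.** .05/5 = .01. The division is exact.

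**2. Count of tests.**
- Yes/no items: 5 levels x 2 roles = 10. This follows from the paragraph itself.
- Ratings: 5 levels x 1 role = 5 if only one role is tested, or 5 x 2 = 10 if both are, as sections 2.2 and 3.3.1 imply.
- Both measures together: 15 to 20, depending on the role split.

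**3. Family-wise error at .01 per test.** The upper bound is k x .01. For independent tests it is 1 - .99^k.

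| Set of tests | k | Upper bound | Independent |
|---|---|---|---|
| One role, one measure | 5 | 5% | 4.9% |
| One measure, both roles | 10 | 10% | 9.6% |
| Both measures, ratings in one role | 15 | 15% | 14.0% |
| Both measures, both roles | 20 | 20% | 18.2% |

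**4. Effect of correlation on the ten yes/no tests.** The same people answer at all levels, and the dyad members are related. In a simulation of normal test statistics, with assumed correlations of .3 to .7 between levels and .1 to .4 within dyads, family-wise error is about 6.5% to 9%.

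**5. Threshold for ten tests.** .05/10 = .005. If the tests are independent, 1 - .995^10 = 4.9%.

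**6. Power cost.** Exact power of the chi-squared test for 90% against 60% interest with 25 per group is 47.9% at .01 and 37.0% at .005. Holm recovers part of the loss: once the smallest p-value passes .005, the next is compared with .05/9 = .0056, and so on.

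**The case against.** The strongest defence is that the sentence order implies five comparisons within each role, with the correction applied afresh to the ratings. On that reading .01 does hold 5% within each set of five. Correcting by outcome and by population is a common choice: the synopsis lists interest and preferences as separate Stage I primary outcomes, and patients and informants are different people reporting on different targets. This stands as a legitimate design. It does not rescue the text, which declares no such family and gives five as the number of comparisons to be conducted. Even with the two measures kept apart, each has ten tests once both roles are included.

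Discreteness gives some protection. With 25 per group and a true rate of 90% in both, the exact size of the chi-squared test at .01 is about .006. At rates of 50% or 75% it is about .010, so this cannot be relied on.

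Three stronger readings might be inferred, and the documents support none of them.

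- **A fixed total of 20 tests, with a threshold of .0025.** The role split for the ratings is not stated in section 3.4.2.1, and section 3.3.1 frames the rating items by risk factor, so the count for that measure is not settled. Pooling the measures also merges outcomes that the synopsis lists separately.
- **A failed promise of 5% control over all of Outcome 1.1.** No sentence makes that promise.
- **Any false race difference passing into the disclosure protocols.** Sections 2.1 and 2.2 give a general link from Stage I results to protocol development. Section 3.3.2 personalises on demographic factors and home location, diagnosis, level of risk and the indicators requested. No rule ties content to a significant race test.

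**Conclusion.** The concern holds in a limited form. The division is right, but the count behind it contradicts the preceding sentence: ten yes/no tests are planned, not five, and the rating tests have no stated divisor or role split. That much needs no assumption.

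At .01 per test, 5% control extends to one role on one measure and no further. Across the ten yes/no tests, error is 9.6% under independence and about 6.5% to 9% under the assumed correlations. The 14% to 18% range requires both pooling the measures and independence, so it should not be quoted as the error rate of the plan. The documents give no power calculation for Stage I, so no stated sample size is affected. The change should be made because this is a primary analysis whose decision threshold rests on the miscounted number.

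**What to change.** In section 3.4.2.1, replace the statement of five comparisons with the actual count for each measure, and state that the rating tests cover both roles. Apply Holm over the ten race tests of a measure (5 levels x 2 roles, first step .05/10 = .005). Name one measure, checklist or rating, as primary and the other as supportive, so that the 5% claim attaches to the primary measure.

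If sets of five by role and measure are preferred, keep .05/5 = .01 as the first step, use Holm within each set, and state that 5% control holds only within each set and not across Outcome 1.1.

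Either route is a change of wording. The first lowers first-step power in the 90% against 60% example from about 48% to 37%, part of which Holm recovers. The second loses no power but supports a narrower claim.
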